3.3 Sample Size

A sample size of 100 completed questionnaires from healthcare providers in each of eight selected countries representing the geographic diversity of the EU is proposed. The size of the sample was determined based on both practical and statistical considerations. There is no presumed target rate for success in risk minimization measures based upon either a process measure (e.g., receiving educational materials) nor is there a rate specified *a priori* for success in outcome measures (e.g., metabolic monitoring). A sample of 100 completed questionnaires will allow estimation of the rate for process and outcome measures with a moderate degree of precision (within 6-10 percentage points regardless of the actual level of the process or outcome measure). The table below shows the precision of the estimates for level process and outcome measure using two-sided 95% confidence intervals (CIs) obtained with the sample size of 100 completed surveys. The noted CIs are used to indicate that for any survey-estimated level of effectiveness of risk minimization, the true population level of effectiveness is at least as high as the lower limit of the 95% CI and may be as high as the upper limit of the 95% CI.

Table 1:Precision of estimated Rates of effectiveness of risk minimization
including: 1) Receiving information (as Process measure) or 2)
performance of metabolic monitoring (as Outcome measure) with a
Sample Size of 100 (Two-sided 95% Confidence Interval)

Estimated Rate	95% Confidence Interval Lower Limit	95% Confidence Interval Upper Limit
1%	0.0%	3%
6%	1.3%	10.7%
11%	4.9%	17.1%
16%	8.8%	23.2%
21%	13%	29%
26%	17.4%	34.6%

Estimated Rate	95% Confidence Interval Lower Limit	95% Confidence Interval Upper Limit
31%	21.9%	40.1%
36%	26.6%	45.4%
41%	31.4%	50.6%
46%	36.2%	55.8%
51%	41.2%	60.8%
56%	46.3%	65.7%
61%	51.4%	70.6%
66%	56.7%	75.3%
71%	62.1%	79.9%
76%	67.6%	84.4%
81%	73.3 %	88.7%

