3.4 Healthcare Provider Recruitment

A random sample of healthcare providers who were targeted to receive SEROQUEL[®] / SEROQUEL[®] XR educational materials and who are considered likely to prescribe SEROQUEL[®] / SEROQUEL[®] XR will be invited to participate. An invitation will be sent to the healthcare providers.

If the required number of completed surveys is not achieved within the expected timeframe of approximately two weeks after the first invitation, a second one will be sent to non-respondents from the original sample with subsequent follow-up to maximize participation. If these efforts do not result in the required number of surveys within three to four weeks, then a new sample of prescribers will be randomly selected.

All participating healthcare providers will be offered a nominal fee consistent with approved market value for the physician's time for a completed survey. The survey is estimated to take less than 10 minutes to complete.

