5. MEASURES TO MINIMIZE BIAS IN THE SAMPLE AND QUESTIONNAIRE ADMINISTRATION

Several measures will be used to minimize bias in the sample. Every effort will be made to ensure diversity in the distribution of healthcare providers invited to participate with regard to geography and physician specialty; however, the choice to ultimately participate in the survey is voluntary.

All participants who might have access to confidential information about this survey will be excluded. Also, Healthcare providers or their immediate family members employed by AstraZeneca or a European Regulatory Agency will not be eligible to participate.

An Internet survey will be convenient for respondents to participate since they can complete the questionnaire at any convenient time and location. Healthcare providers will be provided

with a unique code during the recruitment process and will then be asked to provide the unique code in order to gain access to the online survey. All respondents who are eligible to participate will answer the same questions outlined in Appendix B. The code will be inactivated after use to minimize fraud and reduce the chance of a respondent participating in the survey more than once. In order to minimize self-selection bias, a reminder notice will be sent to invited participants who have not responded within two weeks of the initial invitation.

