6. ANALYSIS

The survey questionnaire contains questions about the specialty of the physician sample completing the survey, questions specific to whether referrals are made to other healthcare providers for metabolic monitoring, whether the healthcare provider conducts monitoring of patients, general questions regarding receipt of the educational materials, and behavior about reading the materials. Information obtained from responses to each question of the survey will be reported as descriptive statistics. A frequency distribution of responses to each question (the number of respondents who give answers to each response option) will be presented.

Each risk minimization behavior will be evaluated individually.

Related behaviors, such as:

- Monitoring for weight
- Monitoring for signs and symptoms of hyperglycaemia and monitoring blood glucose changes in patients with diabetes mellitus will be combined to report the number of survey respondents who answered each risk minimization activity individually, any one activity and both activities. This will be expressed as a percent of the total number of respondents who answered the questions on these risk minimization activities.

Frequency distributions of the responses to having received SEROQUEL[®] / SEROQUEL[®] XR educational materials and behaviors about reading the educational materials, will also be calculated and displayed. The analysis of frequencies will include exact binomial 95% confidence intervals.

The following will be reported, as appropriate, as part of this analysis:

- The number of invitations issued to healthcare providers
- The number of healthcare providers screened for participation
- The number of healthcare providers eligible for participation
- The number of healthcare providers who completed the survey

- Description of healthcare provider survey participants, including:
 - Specialty of respondent
 - Country of practice
- Frequency distribution of responses to each survey question (the number of respondents who give each answer to each question)
- Percent of respondents selecting desired response to each question relating to each risk minimization activity and 95% confidence interval
- Percent of respondents demonstrating success of composite risk minimization activities and 95% confidence interval

Additional analyses may be performed as needed.

Risk Minimization Physician Survey Protocol

Drug Substance	Quetiapine fumarate
Study Code	D1443C000127
Edition Number	1

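### Section 3.3 reads the 95% lower limit as a floor under the true population level; a confidence limit from a voluntary sample of 100 gives no such floor (minor, wording)

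*Protocol*

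**What the plan says.** Section 3.3 plans "A sample size of 100 completed questionnaires from healthcare providers in each of eight selected countries" and shows the precision in Table 1, "using two-sided 95% confidence intervals (CIs) obtained with the sample size of 100 completed surveys". It sets no target rate for process or outcome measures. It then explains how the limits are to be read, and the explanation covers every estimated rate. Of the lower limit it says that "the true population level of effectiveness is at least as high as the lower limit of the 95% CI". Of the upper limit it says only that the level "may be as high as the upper limit of the 95% CI". The lower limit is stated as a fact and the upper limit as a possibility.

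Section 6 plans percentages with intervals and does not say how to read them: "The analysis of frequencies will include exact binomial 95% confidence intervals". The sentence in Section 3.3 is therefore the only statement in the protocol on how to read the limits.

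On who is measured, Section 5 says that "the choice to ultimately participate in the survey is voluntary". Section 3.4 says that if a second invitation and follow-up do not bring in enough questionnaires, "then a new sample of prescribers will be randomly selected".

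**The concern.** Two separate things are wrong with treating the lower limit as a floor.

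- **Sampling error.** A two-sided 95% interval is built so that the true value may lie below the lower limit, nominally in 2.5% of samples. The sentence allows for no such case.
- **Population.** The interval describes random variation among providers who answer. The sentence speaks of the population level, which here means all targeted providers. The number of completed questionnaires is fixed at 100 per country, so the interval has the same width whether 200 or 1,000 providers were invited to obtain them. It carries no information about those who did not answer.

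The survey is part of the effectiveness assessment that the regulator asked for (Section 1). If the sentence were carried into the report, receipt and monitoring among targeted providers would be presented as guaranteed minimum levels. The error runs in the favourable direction.

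**Working it through.** **Inputs.** From Section 3.3: n = 100 per country, eight countries, two-sided 95% intervals, and the limits in Table 1. From Section 6: exact binomial intervals. Response rates are not given, so those below are assumptions.

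**1. Reproducing Table 1.** The Wald formula p ± 1.96 × √(p(1 − p)/100), with the lower limit cut at 0, matches all 17 rows to rounding. For p = 0.81 the half-width is 1.96 × √(0.81 × 0.19/100) = 0.0769, giving 73.3% to 88.7% as printed. The exact binomial interval for 81 of 100 is 71.9% to 88.2%. Table 1 therefore shows Wald limits, while the report will use exact ones, so both are checked.

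**2. How often the truth lies below the lower limit under ideal random sampling.** For a true rate p, add the Binomial(100, p) probabilities of all counts whose lower limit exceeds p.

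| True rate | Exact limits (Section 6) | Wald limits (Table 1) |
|---|---|---|
| 20% | 2.0% | 2.0% |
| 50% | 1.8% | 2.8% |
| 80% | 1.3% | 4.7% |
| 90% | 2.4% | 5.8% |

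Over true rates from 5% to 95%, the range is 0.4% to 2.5% with exact limits and 0.4% to 11.8% with Wald limits. Neither is ever zero.

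**3. One measure across eight countries.** At the nominal 2.5%, the chance that at least one of the eight lower limits lies above its true rate is 1 − 0.975^8 = 18.3%. With exact limits at a true rate of 50% it is 1 − (1 − 0.0176)^8 = 13.2%. Independence is reasonable here because the eight samples contain different providers. Reporting by country is an inference from the sample size of 100 per country; Section 6 does not state it outright.

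**4. Non-response.** Let respondents have a rate of 81%, let r be the response rate, and let non-respondents be d points lower. The population rate is then 81 − (1 − r) × d. It falls below the exact lower limit of 71.93% once d exceeds (81 − 71.93)/(1 − r) = 9.07/(1 − r):

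| Assumed response rate | Gap d at break-even |
|---|---|
| 10% | 10.1 points |
| 20% | 11.3 points |
| 30% | 13.0 points |
| 50% | 18.1 points |

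**5. A second illustration, also on assumed figures.** Take a true rate of 50%, and suppose that providers with the behaviour are k times as likely to respond. The rate among respondents is then 0.5k/(0.5k + 0.5). The exact lower limit lies above the true 50% in 1.8% of surveys for k = 1, 16% for k = 1.25, 46% for k = 1.5 and 90% for k = 2.

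**The case against.** The strongest defence is that the sentence is a loose gloss on a precision table and not a decision rule. It names the 95% interval and presents it as an indication. Section 6 does not repeat it and plans only descriptive percentages with intervals. There is no target rate and no test, so correcting it changes no estimate, interval or table. Self-selection is also recognised elsewhere: invitees are drawn at random, reminders are sent, and the numbers invited, screened, eligible and completed will be reported.

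Most of this stands, and it sets the weight of the point. It does not make the sentence correct. The lower-limit clause has no confidence qualifier of its own, and the contrast with the upper limit makes it read as unconditional. Reminders and replacement samples may reduce bias or fill the quota, but they do not bring non-response inside the interval.

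Two stronger readings are tempting, and the documents do not support them.

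- A reader might count six Question 3 items, four composites and two Question 4 items in eight countries, which makes 96 intervals, and infer a 1 − 0.975^96 = 91% chance of at least one false floor. Section 6 does not say that every item and composite gets an interval by country. Independence also fails, because within a country all items come from the same 100 respondents and the composites are functions of the items.
- A reader might infer that a modest non-response gap makes most of the floors false. This is not shown. If the respondents' true rate is 81% and the population rate is 73.3%, the exact lower limit lies above the population rate in about 36% of surveys. Other assumed gaps give other figures, and the protocol has no response data from which to choose among them. The break-even gaps should also be worked from the exact limit of 71.9% that will be reported, and not from the 73.3% in Table 1.

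**Conclusion.** The sentence is wrong as written and should be replaced. Under ideal random sampling the shortfall is small: at most 2.5% per interval with the planned exact limits, and nominally about 18% for at least one of eight countries on a given measure, if results are reported by country. The larger gap is that the limits set no floor for all targeted providers, because non-response lies outside the interval. How large that is cannot be known from the protocol; the 10 to 18 points at an estimate of 81% rest on assumed response rates and show sensitivity, not a forecast.

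The severity is minor. A reader might take the sentence as a commitment to report guaranteed minimum levels, but no other section adopts it, and nothing in the design or planned analysis depends on it. What changes is what the survey may claim about targeted providers.

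**What to change.** Replace the last sentence before Table 1 in Section 3.3 with:

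*Each interval is the range of levels compatible with the survey estimate at 95% confidence, allowing for random sampling error only; it applies to all targeted providers only if respondents resemble non-respondents.*

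Show each country's response rate beside its intervals, taken from the counts of invitations and completed surveys already planned in Section 6 and split by country. A break-even non-response gap, as in step 4 of the working, is optional.

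The cost is one sentence and one added figure per country. No new data, sample size change or redesign is needed. The downside for the sponsor is a slightly less favourable stated conclusion.

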3.4 Healthcare Provider Recruitment

A random sample of healthcare providers who were targeted to receive SEROQUEL[®] / SEROQUEL[®] XR educational materials and who are considered likely to prescribe SEROQUEL[®] / SEROQUEL[®] XR will be invited to participate. An invitation will be sent to the healthcare providers.

If the required number of completed surveys is not achieved within the expected timeframe of approximately two weeks after the first invitation, a second one will be sent to non-respondents from the original sample with subsequent follow-up to maximize participation. If these efforts do not result in the required number of surveys within three to four weeks, then a new sample of prescribers will be randomly selected.

All participating healthcare providers will be offered a nominal fee consistent with approved market value for the physician's time for a completed survey. The survey is estimated to take less than 10 minutes to complete.

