3.2 Study Population

3.2.1 Inclusion Criteria

Health Care Professionals who were targeted to receive the metabolic educational materials and either currently prescribe or have the potential to prescribe SEROQUEL or SEROQUEL XR.

Each physician should meet all inclusion criteria and none of the exclusion criteria to be eligible for this survey. Under no circumstances can there be any exceptions to this rule.

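### Sections 3.4 and 5 disagree on whether non-respondents are reminded once a country has its 100 completes, so the plan's own step against self-selection may be skipped in fast-filling countries

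*Protocol*

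**What the plan says.** **Target.** Section 3.3 proposes "A sample size of 100 completed questionnaires from healthcare providers in each of eight selected countries", which is 8 × 100 = 800 in all. Precision is shown "using two-sided 95% confidence intervals (CIs) obtained with the sample size of 100 completed surveys".

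**Second contact, Section 3.4.** The rule opens with a condition, "If the required number of completed surveys is not achieved within the expected timeframe of approximately two weeks after the first invitation", and only then does the action follow: "a second one will be sent to non-respondents from the original sample with subsequent follow-up to maximize participation". If the number is still short after three to four weeks, "then a new sample of prescribers will be randomly selected".

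**Second contact, Section 5.** In the section on limiting bias, the protocol says that "a reminder notice will be sent to invited participants who have not responded within two weeks of the initial invitation". The count of completes plays no part in this rule, and its stated purpose is to limit self-selection.

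**Who is sampled.** Section 3.2.1 admits targeted providers who "either currently prescribe or have the potential to prescribe SEROQUEL or SEROQUEL XR". Section 3.1 repeats that population and speaks of approaching a sample of targeted providers. Section 3.4 draws its random sample from targeted providers judged likely to prescribe, and does not say how likelihood is judged.

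**The concern.** One section treats the two-week contact as a way to fill a quota. The other treats it as protection against a sample made up of the most willing. In a country that fills early, field staff cannot follow both. If they follow the recruitment section, the only step that the protocol ties by name to self-selection is left out just where every complete came from someone who answered without prompting.

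The survey is descriptive and sets no success threshold, so the estimated rates of receipt, reading and monitoring are themselves the result. Section 3.3 reads each confidence interval as bounding the true population level. That reading needs a defined population and a consistent way of reaching it. If some countries are reminded and others are not, differences between countries partly reflect how hard providers were pursued.

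The frame wording raises a smaller, separate question: which population the reported percentages describe.

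**Working it through.** **1. The plan's own figure.** Table 1 was recomputed as p ± 1.96 × √(p(1 − p)/100), with the lower limit cut at zero. At p = 0.51 the half-width is 1.96 × √(0.51 × 0.49/100) = 9.8 points, giving 41.2% to 60.8% as printed. All 17 rows agree to rounding. The widest half-width, 9.8 points, fits the upper end of the stated precision, "within 6-10 percentage points regardless of the actual level of the process or outcome measure". These intervals cover sampling error only; who responds, and from which list, does not enter the formula. The discrepancies discussed here leave Table 1 unchanged.

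**2. The two reminder rules side by side.**

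| Completes in a country at about week two | Section 3.4 | Section 5 |
|---|---|---|
| Fewer than 100 | Non-respondents contacted again | Non-respondents reminded |
| 100 or more | No second contact | Non-respondents reminded |

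The rules conflict only in the second row. Two things must both hold before the bias step is lost: Section 3.4 governs, and the country reaches 100 by about week two.

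**3. Can the effect be sized?** Let e be the share of early responders among everyone who would respond if reminded, and d the early-minus-late difference in a rate. Stopping at early responders shifts the estimate, relative to the reminded sample, by (1 − e) × d. The protocol gives neither e nor d, nor any response rate or number to invite from which e could be guessed. The sign of d is also unstated. Moreover, the reminded sample still consists of volunteers, so this shift is not the bias against the population.

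**4. The frame.** Let s be the share of eligible providers who are judged likely to prescribe, and d′ the difference in a rate between them and the other eligible providers. Sampling only the likely group shifts the estimate from the Section 3.2.1 population by (1 − s) × d′. Both inputs are assumptions:

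- s = 0.9, d′ = 5 points: 0.1 × 5 = 0.5 points
- s = 0.7, d′ = 10 points: 0.3 × 10 = 3.0 points
- s = 0.5, d′ = 20 points: 0.5 × 20 = 10.0 points
- d′ = 0: no shift, whatever s is

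The range runs from nothing to about the widest half-width. It shows only that the document does not settle the matter.

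**The case against.** **The conflict may never arise.** Nothing in the protocol suggests that any country would reach 100 within two weeks; below 100, both sections send the contact. Nor does the protocol say that the survey closes at 100, so late completes might be accepted anyway. This stands, and it is why over-representation of early responders is a possibility and not a finding. It does not remove the need to say which rule applies.

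**The two contacts could be different things.** One might read a reminder to everyone, plus a second invitation where numbers are short. But both fall at two weeks and go to the same people, and the recruitment section mentions no unconditional reminder. If two contacts are meant, the plan should say so.

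**The replacement sample.** A reader might infer from "then a new sample of prescribers will be randomly selected" that replacements need not have been targeted with the materials. The document does not support this. Being targeted is an inclusion criterion without exceptions in Section 3.2.1, and the screening module in Section 4.2 checks all inclusion criteria before anyone continues.

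**The narrower frame may be sensible.** Questions 2 and 3 ask about the respondent's own patients on the product, so a provider without such patients has little to report. Inviting a subset of eligible providers also does not contradict an eligibility rule. Both points stand. What remains is that the population is described in two ways and the narrower term is undefined.

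**Conclusion.** The contradiction between Sections 3.4 and 5 is real but limited. It affects only a country that has 100 completes by about week two, and there following Section 3.4 would omit the plan's stated measure against self-selection. Early responders may then be over-represented, and follow-up may differ between countries.

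A reader might go further and infer that the rates are biased upward by about as much as the planned precision. The document does not support that. Such a figure would come wholly from assumed rates for early and late responders, and the upward direction, though plausible, is not shown.

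The frame wording is a separate inconsistency of scope. Read literally, eligible providers not judged likely to prescribe cannot be selected. The effect on the estimates is unknown and could be nil.

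**What to change.** **Reminder.** Amend Section 3.4 so that every non-respondent in an invited sample receives the reminder at two weeks, whether or not 100 completes have been reached, in line with Section 5. State that completes arriving after it are accepted. Report the key results before and after the reminder. The numbers invited, screened, eligible and completed are already to be reported under Section 6, so only the before-and-after split is new.

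**Frame.** Use one description of the sampling frame in Sections 3.1, 3.2.1 and 3.4. If the sample is meant to be limited to likely prescribers, say how that is judged. In either case, state the results for the frame actually sampled.

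**Cost.** Wording changes, automated messages, a few completes and fees beyond 100, and a somewhat longer field period in fast-filling countries. Releasing invitations in small batches with fixed windows is not needed for this and would lengthen fieldwork considerably.

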1. BACKGROUND

The MEB, as the Reference Member State (RMS) for SEROQUEL and SEROQUEL XR, requested AstraZeneca to update the education materials in scope of the EU Risk Management Plan (RMP) and Summary of Product Characteristics (SmPC) changes with respect to hyperglycaemia and metabolic monitoring. The content and the messages for these educational materials have been agreed and distribution in the individual member states is ongoing.

AstraZeneca was also requested to provide a plan for assessing the effectiveness of these educational materials. During discussion with the MEB, it was communicated that there are 2 components to the assessment of effectiveness: process indicators (receipt and understanding of materials) and outcome indicators (changes in behaviour and effect on patients). To realize these 2 indicators, AstraZeneca is proposing 2 components for the evaluation of the effectiveness of the metabolic education: an objective, easy to understand and complete healthcare provider survey and the use of an Electronic Medical Records approach, as a potential means to assess the monitoring of patients.

This protocol describes the evaluation of the effectiveness of the distribution of metabolic educational materials sent to healthcare providers in the EU. It will be conducted via an evaluation survey that uses a questionnaire to assess the receipt of the educational material, whether the material was read, and to assess healthcare provider behaviour regarding the conduct of monitoring of metabolic parameters for patients treated with SEROQUEL and SEROQUEL XR. The survey will be conducted among healthcare providers who were targeted to receive the educational materials following local guidance and directives.

A companion proposal describes the evaluation of electronic medical record (EMR) data including details on objectives, the source of data, and the target healthcare provider-base for the database assessment.

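### The receipt rate describes only providers who were reached and completed the survey, so Section 3.3 cannot treat its lower confidence limit as a floor for all targeted providers

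*Protocol*

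**What the plan says.** Section 1 describes the survey as an "evaluation of the effectiveness of the distribution of metabolic educational materials sent to healthcare providers in the EU". Receipt is one of the process indicators and is measured by Question 4A alone (Section 3.1.1 and Appendix B), so it is known only for providers who complete the questionnaire.

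Section 3.3 sets the target: "A sample size of 100 completed questionnaires from healthcare providers in each of eight selected countries". Section 3.4 starts from "A random sample of healthcare providers who were targeted to receive" the materials and who are considered likely to prescribe. Non-respondents get a second invitation and follow-up. If that is not enough within three to four weeks, "then a new sample of prescribers will be randomly selected". Section 5 offers the reminder as the step against self-selection.

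Section 6 lists the recruitment counts to be reported, beginning with "The number of invitations issued to healthcare providers" and followed by those screened, eligible and completed. It plans exact binomial 95% intervals. Section 3.3 interprets the interval as meaning that "the true population level of effectiveness is at least as high as the lower limit of the 95% CI".

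**The concern.** In most surveys non-response is a general nuisance. Here the quantity being estimated is itself a form of contact success. A provider with a wrong or outdated entry in the target list may miss the mailing and then the invitation. The filter that decides who can answer may therefore overlap with the failure the survey is meant to detect.

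Replacement does not create this problem and does not cure it. Assuming the new sample comes from the same targeted group, it passes through the same filter. It restores the number of completed questionnaires and leaves the rate conditional on being reached and willing to answer. Because the planned counts put undeliverable invitations and refusals together, the report could not show how much of the shortfall was contact failure.

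At stake is whether the survey can say that distribution reached the targeted providers, or only that those who answered recall receiving the materials.

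**Working it through.** **Inputs from the protocol.** n = 100 completed questionnaires per country, two-sided 95% intervals, and stated precision "within 6-10 percentage points regardless of the actual level of the process or outcome measure" (Section 3.3); exact binomial limits in the analysis (Section 6). The protocol gives no response rate, contact rate or share of undeliverable invitations, so these are assumed over a range.

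**Step 1: the plan's own figures.** The limits in Table 1 are p ± 1.96 × √(p(1 − p)/100), with the lower limit cut at 0. For 81%: 1.96 × √(0.81 × 0.19/100) = 7.7 points, giving 73.3% to 88.7%. For 51%: 9.8 points, giving 41.2% to 60.8%. All 17 rows reproduce to rounding. The formula contains only sampling error; nothing in it represents non-response.

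**Step 2: shared contact failure.** Let p be receipt among reachable providers, u the unreachable share of the targeted population, and r receipt among the unreachable. Assume reachable providers respond regardless of receipt and report it correctly. The survey then estimates p, while the targeted population has

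true receipt = (1 − u) × p + u × r.

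Coverage is the Binomial(100, p) probability of those counts x whose exact 95% interval contains the true receipt. For example, with p = 0.80, u = 0.10 and r = 0, true receipt is 0.90 × 0.80 = 72%. The exact interval contains 72% for x = 63 to 81, and that range has probability 63.8% when p = 0.80.

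Results for p = 80% (the exact interval for 80/100 is 70.8% to 87.3%):

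| Unreachable share u | True receipt, r = 0 | Coverage | True receipt, r = 50% | Coverage |
|---|---|---|---|---|
| 5% | 76% | 87% | 78.5% | 95% |
| 10% | 72% | 64% | 77% | 92% |
| 15% | 68% | 26% | 75.5% | 87% |

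For p = 90% and the same three values of u, coverage is 79%, 30% and 7% with r = 0, and 94%, 79% and 68% with r = 50%. With r = p there is no bias.

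**Step 3: a second model, with either direction allowed.** Let π be true receipt and k the ratio of the completion probability in receivers to that in non-receivers. Then

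observed receipt = πk / (πk + 1 − π).

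With π = 60%:

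- k = 1.5: 0.90/1.30 = 69.2%, an excess of 9.2 points.
- k = 2: 1.20/1.60 = 75.0%, an excess of 15 points; the exact interval for 75/100 is 65.3% to 83.1% and misses 60%.
- k = 1: 60%, no bias.
- k = 0.8: 0.48/0.88 = 54.5%, a deficit of 5.5 points.

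A moderate link between receipt and completion can therefore match or exceed the stated 6 to 10 points of precision. A link in the other direction lowers the rate. In both models the new samples leave k, u and r unchanged.

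**The case against.** A reader might infer that receipt is overstated, in the sponsor's favour. The documents do not support that as fact, for four reasons.

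- The protocol does not say how invitations are sent or from which contact details. Question 4A allows for materials that came by mail or from a company representative, so a failed invitation does not imply that the materials were missed.
- Receipt is self-reported for a named month in 2012, with a not-sure option. Forgotten receipt lowers the observed rate.
- Retired providers are not distribution failures for this survey. Section 3.2.1 requires current or potential prescribing, and Section 3.4 restricts invitations to likely prescribers. Only eligible but unreachable providers matter.
- Section 3.4 replaces non-respondents in general. It has no rule aimed at unreachable providers, and replacement is not the source of any bias.

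A reader might also take the completer rate multiplied by (1 − undeliverable share) as the receipt rate for the targeted list. It is not. It sets receipt among undeliverable providers to zero and ignores those who got the invitation and did not answer.

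These objections stand and remove any claim about direction. It can also be said that a crude response rate can be derived from the Section 6 counts, and that outcome coding could sit in a later document. The first is true, but a crude rate does not separate contact failure from refusal. The second carries less weight: outcomes not recorded during fieldwork may not be recoverable at analysis, and the Section 3.3 sentence is protocol text that a later document would not change.

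**Conclusion.** The point holds in a limited form. The receipt rate is estimated among reached and willing completers, the plan collects nothing that shows whether those lost differ, and the interval covers sampling error only. If contact failure is shared between the materials and the invitation, the rate is too high for the targeted population. Under the assumed 80% receipt among reachable providers and 5% to 15% unreachable, the excess is 4 to 12 points if none of the unreachable received the materials, 1.5 to 4.5 points if half did, and zero if they received them equally often. No document supports a particular value of these assumptions, and the net direction is unknown once recall error is allowed for. What can be said firmly is that Section 3.3 claims too much when it reads the lower limit as a floor for the population.

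**What to change.** In Sections 3.4 and 6, log each invitation as undeliverable (returned or bounced), delivered without response, or answered. Report the counts by country and by original or replacement sample. Set aside entries known to be ineligible, such as retired providers. State which channel and contact details the invitations use and whether the materials used the same ones.

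Keep the completer rate as the estimate. Beside it, report completer rate × (1 − undeliverable share among entries not known to be ineligible). For example, 80% with 10% undeliverable gives 0.80 × 0.90 = 72%. Label it a sensitivity bound that assumes no receipt among undeliverable providers and does not correct for delivered non-response.

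Reword Section 3.3 so that the interval is said to reflect sampling error only and to apply to reachable, responding providers.

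The cost is bookkeeping during fieldwork, one extra row per country, and a somewhat less favourable statement of what the survey shows. Sample size and questionnaire stay as they are.
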